A Prospective Study of Hepatitis B Virus (HBV) Immunity and Hepatitis B Vaccination in Patients with Non Alcoholic Fatty Liver Disease (NAFLD) in Canada

Scientific Rationale

The Global Burden of Hepatitis B and HBV Vaccination in Canada:

The hepatitis B virus (HBV) is truly a global human pathogen that affects at least 2 billion people worldwide including ~240 million chronic hepatitis B (CHB) carriers that are at risk for end-stage liver disease ¹. The diagnosis of CHB is confirmed by the persistence of the HBV surface antigen (HBsAg) in serum for >6 months. However, a latent form of HBV infection known as occult hepatitis B infection (OBI) characterized by low-level viremia (i.e., HBV DNA < 200 IU/ml) despite undetectable serum HBsAg has been described with unclear clinical consequences ².

A safe and effective HBV vaccine has been available for ~3 decades and consists of recombinant HBsAg which contains the major viral antigenic epitopes and induces a protective neutralizing antibody to HBsAg (anti-HBs) response in >85% of children vaccinated. Canada is a low HBV-endemic region and in Alberta, and Ontario, public health uses maternal screening for HBsAg to identify babies at-risk for CHB. Thus, all infants born to HBsAg (+) mothers are given passive-active immunoprophylaxis with hepatitis B immune globulin (HBIG) and the HBV vaccine within 12 hours of birth, as well as 2 doses at ~2 and ~6 months of age. Testing of the infants for anti-HBs is recommended at 9 months to ensure immunity. In the late 1990's, a universal HBV childhood vaccination program was initiated in all Canadian provinces and jurisdictions. In Alberta and in Ontario, school-age children are scheduled to receive the 3-dose HBV vaccine series in grade 5. However there remain a significant proportion of adult

Canadians (i.e., born before 1985) who missed childhood vaccination programs. Although current guidelines recommend that certain high-risk populations receive hepatitis B immunization (**Table 1**), appropriate identification and compliance is generally much lower in adults compared to children.

According to the most recent Canadian Association for the Study of Liver Disease guidelines ³, all adults with diabetes, as well as all patients with chronic liver disease should receive the hepatitis B vaccine. The basis for these recommendations are two-fold, (1) diabetics may be at risk of blood-borne virus (BBV) exposure through contact with contaminated blood glucose monitoring devices and (2) diabetic patients are at increased risk of the metabolic syndrome and the development of non-alcoholic fatty liver disease (NAFLD). The improvement in blood glucose monitoring devices, and increased knowledge has reduced the risk of BBV exposure in patients with diabetes. Further, our initial seroepidemiological survey of acute HBV outbreaks in Alberta revealed a decreasing prevalence in diabetic patients (**unpublished data, see Table 2**). Therefore the main incentive for HBV vaccination in diabetics is due to the concomitant risk of the metabolic syndrome and advanced liver disease due to NAFLD. There is limited data on HBV vaccination in NAFLD patients. In 1 Polish study on HBV vaccination in adults ⁴, good response to the HBV vaccine was observed in the patients with liver steatosis. As expected, patients with cirrhosis responded much less favorably to the hepatitis B vaccine than patients with liver steatosis. In addition, in an older study, obesity was also identified as a poor predictor of response to hepatitis B vaccination in pre-adolescents ⁵. Further studies are required in a North American adult (Canadian population).

The Clinical Spectrum of Nonalcoholic Fatty Liver Disease (NAFLD) / and Non Alcoholic Steatohepatitis (NASH):

NAFLD refers to the spectrum of disease and liver damage associated with hepatic steatosis. Patients can have simple steatosis, inflammation and fibrosis, or even cirrhosis. NASH, or non-alcoholic steatohepatitis, refers to the presence of inflammation and/or fibrosis in the presence of steatosis. The prevalence of NAFLD varies widely, but in North America, it is estimated to be anywhere from 10-46%, with the prevalence of NASH ranging from 3-5% in the average population ^{6,7}. NAFLD, and NASH, are most commonly seen in patients who are obese, diabetic, or have other features of the metabolic syndrome (defined as the presence of 3 of the following: abdominal obesity, hypertriglyceridemia, low HDL, insulin resistance/diabetes, and hypertension).

Obesity is a growing epidemic in North America, with rates of obesity in the adult population increasing from a national average of 13% in 1962 to 34.9% in 2012 ⁸. Since diabetes is closely related to obesity, rates of diabetes have also risen accordingly, with 9.3% of the US population, or 29.1 million people, having diabetes, although an estimated 27.8% of people are undiagnosed (CDC National Diabetes Statistics Report 2014).

The pathophysiology of NASH is thought to be due to a multi-hit model, although it has not been fully explained. The initial hit, or insult, is thought to be secondary to steatosis. Steatosis, which arises from triglyceride accumulation, can be due to abnormal free fatty acid metabolism (either increased import into the liver, decreased export out of the liver, or abnormal beta-oxidation) ⁹. Increased delivery is often seen in settings such as obesity, excess carbohydrate and fat consumption, or rapid weight loss. Defective secretion of triglycerides is often seen in patients with gene mutations resulting in abnormal cholesterol metabolism ¹⁰. The

A Prospective Study of Hepatitis B Virus (HBV) Immunity and Hepatitis B Vaccination in Patients with Non Alcoholic Fatty Liver Disease (NAFLD) in Canada. Protocol, Version 3, 13-June-2019. [name] Page **3** of **18**

second insult is thought to result in inflammation and eventually fibrosis. Some of the main mechanisms behind steatohepatitis are abnormal fatty acid β -oxidation and oxidative injury. Insulin resistance plays a role in both the development of hepatic steatosis and steatohepatitis, even in non-obese patients¹¹. In the obese patient, as visceral adipose tissue increases, peripheral and hepatic insulin resistance develop and worsen, resulting in hepatic steatosis and inflammation^{11,12}. Obese patients have more visceral fat, which in turn is associated with higher levels of inflammation and pro-inflammatory cytokines¹³. Obesity, older age, Hispanic origin, diabetes, and the presence of inflammation and/or fibrosis on biopsy are predictors of progression to cirrhosis¹⁴⁻¹⁷. As with other hepatic diseases, the presence of multiple hepatic processes resulting in inflammation hastens the development of fibrosis. Therefore, in patients with NAFLD, the development of acute or chronic hepatitis B infection can result in an increased risk of development of cirrhosis. Studies have shown that in pediatric patients with NAFLD, rates of non-immunity to hepatitis B are alarmingly high, approaching nearly 50%¹⁸. Although there have been many studies examining the prevalence of serological immunity to hepatitis B in patients with alcoholic liver disease, and the effect of concomitant infection in addition to the liver disease, no such similar studies exist examining the prevalence of hepatitis B antibodies in the adult population with NAFLD.

In summary, there is a paucity of recent studies on HBV serology and HBV vaccine responses in adults, especially in the context of obesity and NAFLD. We propose that adults with NAFLD should undergo comprehensive screening for hepatitis B immunogenicity, in addition to screening for infection, and catch up or booster vaccinations should be administered to non-immunized patients with confirmatory immunity testing thereafter.

Hypotheses/Aims:

(1) Due to missed childhood vaccination programs, the majority of adult patients with NAFLD in Canada do not have immunity to hepatitis B. (2) Adults with NAFLD who receive the HBV vaccine have reduced immunogenic responses in the setting of obesity (i.e., protective anti-HBs titres). **Aims:** (1) To determine the sero-prevalence of immunity against hepatitis B in a cohort of prospectively evaluated adult NAFLD patients. (2) To prospectively determine HBV vaccine responses (anti-HBs titres) in adult NAFLD patients.

3.0: Study Design and Methods

Study Population:

Study Population, Clinical Assessment, Inclusion/Exclusion Criteria:

Patients will be recruited from large tertiary liver clinics in Canada (Dr. [name], University of Calgary, [name] University of Alberta, [name], University of Ottawa, [name], LAIR Centre Vancouver, and [name], St. Paul's Hospital, BC) and following signed informed consent will be prospectively enrolled under an approved ethics protocol according to the declaration of Helsinki. Multi-site data will be collected using a web-based electronic report form in a secure computing environment custom developed by the PI and funded by a Canadian Foundation for Innovation infrastructure grant. Baseline data collected will include: (i) epidemiological information such as, age, sex, alcohol use, smoking; (ii) anthropometric data (body mass index, BMI, and waist circumference), (iii) liver disease lab tests such as, complete blood count, transaminases and other liver function tests, liver imaging, and non-invasive assessment of liver fibrosis via transient elastography (i.e., TE, FibroScan®), liver biopsies, and inflammatory markers associated with disease progression (ferritin, hemoglobin A1C, HbA1C, lipid profile), (iv) HBV serology including HBsAg, anti-HBs titres

A Prospective Study of Hepatitis B Virus (HBV) Immunity and Hepatitis B Vaccination in Patients with Non Alcoholic Fatty Liver Disease (NAFLD) in Canada. Protocol, Version 3, 13-June-2019. [name] Page 5 of 18

and total HBV core antibody (anti-HBc) by conventional assays (iv) tests for exclusion of other liver diseases (i.e., HCV, autoimmune hepatitis, alpha 1 antitrypsin deficiency, hemochromatosis etc.) and, pregnancy. The investigators have access to large patient cohorts and are ideally positioned to perform this study. The Calgary Liver Unit services a catchment area of two million individuals and receives approximately 40 to 60 new NAFLD referrals a month, or approximately 20% of all new hepatology referrals. Inclusion criteria: Subjects 18-60 years of age, who provide signed informed consent, with a diagnosis of NAFLD/NASH according to expert assessment (by imaging, TE, abnormal lab tests and/or liver biopsy) and no evidence of prior infection or immunity to hepatitis B (negative HBsAg, anti-HBs, anti-HBc). Exclusion criteria: Subjects < 18 years of age, refused vaccination, have documented immunity / prior exposure to hepatitis B (i.e., positive for anti-HBs, anti-HBc, HBsAg), pregnancy, HIV-positive, decompensated cirrhosis (i.e., Child-Pugh Class B or C) due to impact on immune response. Subjects >60 y will be excluded, due to effect of age and reduced response to HBV vaccination. The results of a recent pooled analysis of GSK clinical trial data (N=2620, total vaccinated cohort) showed a statistically significant decrease with age in sero-protection rates, and a predictive model that showed the anti-HBs sero-protection rate remains $\geq 90\%$ up to 49 y of age and $\geq 80\%$ up to 60 y of age ¹⁹.

Study Design and Outcomes

Following initial clinical investigations (i.e., labwork and transient elastography as described above), patients are triaged as low, moderate, or high risk based on expert clinical consensus opinion and current clinical trial protocols in NAFLD/NASH. Low risk patients are those who do not have any risk factors for fibrosis progression, liver decompensation or HCC, or development of NAFLD complications, based on presence of dyslipidemia, diabetes, and HbA1C

A Prospective Study of Hepatitis B Virus (HBV) Immunity and Hepatitis B Vaccination in Patients with Non Alcoholic Fatty Liver Disease (NAFLD) in Canada. Protocol, Version 3, 13-June-2019. [name] Page 6 of 18

levels (**Table 3**). These patients then attend a 3-hour teaching session with a dedicated NAFLD nurse clinician, a dietician, an exercise counselor, and also a social worker. Patients who have risk factors for progression to fibrosis, or who already have fibrosis are seen in clinic by a hepatologist. Finally, patients with metabolic syndrome, poorly controlled diabetes or hyperlipidemia that is difficult to treat are seen in a multidisciplinary clinic by a hepatologist and dedicated general internist with an interest in vascular risk modification. Thus, the highest risk patients are seen by multiple specialists in order to maximize care of all their medical issues, especially as they relate to NAFLD and NASH. Currently, no other clinics of this kind (either the low risk or multidisciplinary clinics) exist of their kind in Canada.

Baseline HBV Serology Testing and HBV Vaccination in Patients with NAFLD/NASH:

All subjects enrolled will be assessed for HBV serology by conventional immunoassays (i.e., HBsAg, anti-HBs, anti-HBc) to determine the prevalence of protective HBV immunity, either from natural exposure or immunization. At-risk individuals will be prospectively immunized for hepatitis B with standard dose of vaccine as per standard of care, at 0, 1 and 6 months (20 microgram intramuscular). Patients will be subsequently tested at 7 months (~1 month after completion of the vaccine series) for anti-HBs titres by conventional enzyme immunoassay (EIA, Abbott Architect). If titres are low, subjects will be given a second round of a series of 3 vaccinations, as per guidelines and re-tested for anti-HBs titres. Additionally, PBMC will be isolated from ~ 40 - 60 ml of peripheral blood according to standard protocol on Ficoll density gradient centrifugation at 2 time-points: (1) prior to first vaccine dose and (2) following the 3rd vaccine dose, at the time of serological testing for anti-HBs titres. All PBMC samples will be cryopreserved in liquid nitrogen until use, under conditions optimized in our lab

for storage and recovery of PBMC for functional studies. To assess HBV specific T and B cell responses, cryopreserved PBMCs will be thawed, re-suspended in RPMI/fetal calf serum and stimulated in quadruplicates of 3×10^5 cells/well with a 5 µg/ml recombinant HBsAg (American Research Products, Waltham, MA), a negative control HCV peptide pool (*kindly provided by Dr. [name]*), and 1 µg/ml of phytohemagglutinin (PHA; Invitrogen, Carlsbad, CA) or DMSO. HBV memory B-cell responses will be determined by an HBsAg-IgG B cell enzyme linked immunospot (ELISpot assay). IFN-gamma-secretion by HBV specific T cells will also be enumerated by ELISpot¹⁹. The number of specific spots (i.e., the number of spots in the presence of antigen minus the number in the absences of antigen) will be determined and a positive HBsAg specific T cell responses defined as >3-fold than the negative control (DMSO) background response and compared to the baseline (i.e., prior to vaccination) PBMC sample²⁰. The PBMC cell supernatant released from unstimulated and stimulated cells will also be collected at 72 hours and cytokine secretion^{21,22} (i.e., IL-2, IL-4, IL-10, TNF-alpha, IL-6, and IFN-gamma etc.) quantified using commercially available ELISA kits according to manufacturers protocol. All laboratory investigations are considered standard of care except for the extra blood draw for PBMC isolation and further testing as noted. All subjects will be monitored after each vaccine dose for possible adverse events (A/Es), as per standard clinical care. Most A/Es expected are mild (i.e., injection site redness).

4.1.3. Sample Size Calculation and Data Analysis Plan:

The primary objective of the study is to determine how NAFLD-associated metabolic risk factors and liver inflammation / fibrosis affects vaccine response. The primary outcome is anti-

A Prospective Study of Hepatitis B Virus (HBV) Immunity and Hepatitis B Vaccination in Patients with Non Alcoholic Fatty Liver Disease (NAFLD) in Canada. Protocol, Version 3, 13-June-2019. [name] Page **8** of **18**

mean \pm standard deviation for continuous data while for categorical data it will be presented as proportions. The chi-square and Fisher exact tests will be used to look at the association between immunological responses with the categorical variables. Comparisons of mean anti-HBs titres for patients with and without protective antibodies, ELISpot data and cytokine responses, within and between groups will be made using Student's t-test and analysis of variance (ANOVA) if the distribution is normal, while the Mann-Whitney U test and Kruskal-Wallis tests will be used if normality assumption is violated. The association between obesity as well as NAFLD and vaccine response will be analyzed using a logistic regression model adjusting for known factors impacting vaccine responses (i.e., age, co-morbidities).

4.1.4. Potential Limitations of HBV Vaccination Studies in NAFLD/NASH Patients: Some subjects may be lost to follow-up or refuse participation (i.e., due to religious or cultural objections to vaccination). Additionally some patients may decline to undergo a liver biopsy, which is important to confirm a histological diagnosis of NAFLD/NASH. However, it is standard practice for the PI to perform liver biopsy on all patients in which TE cannot be accurately performed (i.e., due to obesity) or if there is elevated liver stiffness suggesting at least moderate fibrosis. Additionally, the non-invasive markers (i.e., TE, ferritin, transaminases) and presence of metabolic risk factors are accepted surrogates in clinical practice and often used to base decisions on the need for a liver biopsy and eligibility for NASH/NAFLD clinical trials. Regardless, any data obtained will generate novel data on the severity of liver histology and HBV vaccine responses. Previously, the referring physician (i.e., family Dr.) was asked to immunize the patients, which may have affected compliance and follow-up. We plan to vaccinate patients in the specialist hepatology / infectious disease clinic. A clinical research study coordinator will be responsible for contacting the patients in follow up and to provide

A Prospective Study of Hepatitis B Virus (HBV) Immunity and Hepatitis B Vaccination in Patients with Non Alcoholic Fatty Liver Disease (NAFLD) in Canada. Protocol, Version 3, 13-June-2019. [name] Page **10** of **18**

reminders for vaccine appointments and blood work (within 1 month due to natural anti-HBs decline after vaccination). People may be more willing to be vaccinated if prescribed by a specialist since the cost is covered by health care plan. The investigators have access to large cohorts and are ideally positioned to perform this study. The Calgary Liver Unit services a catchment area of two million individuals and receives approximately 40 - 60 new NAFLD referrals a month, or ~20% of all new hepatology referrals to our group, and similar numbers are seen in other sites. This study does not include a healthy adult control arm, due to the nature of our patient population referred who usually has underlying liver disease. However, the results can be compared to data available from multiple large vaccine efficacy clinical trials in healthy adult individuals conducted by our industry partner (GlaxoSmithKline, GSK) ¹⁹.

Expertise and Support:

[name] (MD, MSc, Assistant Professor of Medicine) is a hepatologist with a dedicated clinical and research interest in hepatitis B. [name] holds a CIHR New Investigator Award and is appointed to the World Health Organization Expert Advisory Panel for Essential Medicines. She co-authored the Canadian Association for the Liver Disease (CASL) guidelines on Management of Chronic Hepatitis B. She has published extensively in both HBV molecular and clinical studies and has the wet-laboratory and clinic infrastructure (i.e., clinical database, bio-banking) to support her research. [name] (PhD, Assistant Professor of Medicine). [name] holds a Tier 1 Canada Research Chair on Intravital Imaging in Infections. He has expertise in the role of innate immunity in viral infections. [name] has collaborations with [name] for HBV transgenic mice model (see letter of support). The Canadian HBV Network:

(Drs. [name], MD; [name], MD; [name], MD; [name], MD, [name], PhD; [name], MD; A Prospective Study of Hepatitis B Virus (HBV) Immunity and Hepatitis B Vaccination in Patients with Non Alcoholic Fatty Liver Disease (NAFLD) in Canada. Protocol, Version 3, 13-June-2019. [name] Page 11 of 18

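### The only regression names NAFLD as an exposure although every subject has it, and the inflammation/fibrosis part of the primary objective has no defined adjusted analysis

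*Combined protocol and SAP*

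**What the plan says.** - **Objective** (section 4.1.3): "The primary objective of the study is to determine how NAFLD-associated metabolic risk factors and liver inflammation / fibrosis affects vaccine response".
- **Model** (section 4.1.3, last sentence): "The association between obesity as well as NAFLD and vaccine response will be analyzed using a logistic regression model". It adjusts for age and co-morbidities. The sample-size paragraph of the same section gives a longer adjustment list that adds sex and BMI. Neither list contains a fibrosis or inflammation measure.
- **Eligibility** (section 3.0, inclusion criteria): subjects enter "with a diagnosis of NAFLD/NASH according to expert assessment".
- **Comparator** (section 4.1.4): "This study does not include a healthy adult control arm". Results may be set beside outside trials in healthy adults, but that comparison is not part of the regression.
- **Data available** (section 3.0, baseline data): elastography, liver biopsies, transaminases, ferritin, HbA1C and lipids.
- **Other tests** (section 4.1.3): chi-square or Fisher tests of immunological response against categorical variables, and t-test/ANOVA or rank tests within and between groups. None names fibrosis or inflammation, and none is adjusted.

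**The concern.** A model can estimate the effect only of something that varies among the subjects. Presence of NAFLD does not vary here, so taken at its word the plan names two associations and can deliver one. The analyst would find the term dropped or flagged by the software and would have to choose a replacement, possibly with titres already in hand. Biopsy stage, stiffness, ferritin, transaminases and triage level are all candidates. At stake is the liver half of the stated primary objective, which would have either no adjusted estimate or one whose exposure was chosen after the results were known.

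**Working it through.** **The plan's own figure.** The plan gives no precision or power for a liver exposure. Its claim of 80% power at 5% Type I error with 70 subjects comes without an effect size, SD, response rates or group split, so it cannot be reproduced. Stratification is by obesity group only.

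**Step 1: literal reading.** With NAFLD = 1 for everyone,

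logit(p) = b0 + bN·1 + bO·obesity + bA·age + bC·co-morbidity = (b0 + bN) + bO·obesity + bA·age + bC·co-morbidity.

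Only the sum b0 + bN is identified. A design matrix for 70 subjects with columns intercept, NAFLD, obesity, age and one co-morbidity has 5 columns and rank 4. bO does not involve the split between b0 and bN, so the obesity coefficient is the same with or without the NAFLD column.

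**Step 2: severity reading.** The background section on the clinical spectrum says "NAFLD refers to the spectrum of disease and liver damage associated with hepatic steatosis", so severity may well be what was meant. Possible codings in the document:

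| Candidate | Where | Difficulty as a default |
|---|---|---|
| Biopsy stage | 3.0, 4.1.4 | Done selectively: where elastography fails (e.g. because of obesity) or stiffness is raised |
| Elastography stiffness | 3.0 | No cut-off or coding given |
| Ferritin, transaminases | 3.0, 4.1.4 | Neither assigned to an analysis |
| Triage level | Study Design and Outcomes | Mixes metabolic and liver factors |

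On triage, "patients are triaged as low, moderate, or high risk based on expert clinical consensus opinion". Low risk is judged "based on presence of dyslipidemia, diabetes, and HbA1C" levels, and then "Patients who have risk factors for progression to fibrosis, or who already have fibrosis are seen in clinic by a hepatologist". Such a variable would not separate the metabolic part of the objective from the liver part. Table 3, cited for the triage, is not in the text available, so its criteria could not be checked.

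To illustrate the open choice: five independent tests at 5% give 1 − 0.95^5 = 0.23 probability of at least one false positive. These five candidates are correlated, so the true figure would be lower.

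**Step 3: what a named fibrosis variable could show.** Take a linear model of log10 titre with fibrosis, BMI, age, sex and diabetes, so 70 − 6 = 64 residual degrees of freedom and t = 1.998. Half-width in residual SD = t × sqrt(1/n1 + 1/n0). Prevalence and shared variance are assumptions; the document gives neither.

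| Assumed prevalence | n1 v n0 | Half-width | With 20% shared variance (÷ sqrt 0.8) |
|---|---|---|---|
| 20% | 14 v 56 | 0.597 | 0.667 |
| 30% | 21 v 49 | 0.521 | 0.583 |
| 50% | 35 v 35 | 0.478 | 0.534 |

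**Step 4: why titre rather than the 10 mIU/ml threshold.** Section 3.0 cites seroprotection of at least 90% up to age 49 and at least 80% up to age 60 in outside vaccine-trial data. At 80-90% response, 70 subjects give 70 × 0.10 = 7 to 70 × 0.20 = 14 non-responders. At an assumed 60-70% they give 21 to 28. With 30% fibrosis, equal response in both groups and no covariates, SE(log OR) = sqrt[1/(21pq) + 1/(49pq)], where p is the non-response rate and q = 1 − p. This is 0.869 at p = 0.10 and 0.652 at p = 0.20, so the 95% limits lie a factor exp(1.96 × SE) = 5.5 or 3.6 either side of the odds ratio.

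**The case against.** The best defence is that NAFLD in the model sentence means NAFLD severity. The document describes a spectrum, triages patients by risk and expects to learn about histological severity and vaccine response. On that reading nothing is constant and the rank result does not apply. This is plausible, and it shifts the defect from an inestimable term to an undefined one. It does not remove it, because no measure, coding or cut-off is attached.

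Second, the generic unadjusted tests could be applied to fibrosis groups. That is true, so a reader should not infer that fibrosis is left with no analysis at all. The gap is in the adjusted analysis.

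Third, this is a convenience pilot stratified by obesity, and the hypotheses and aims do not mention fibrosis. That limits the weight of the point, but section 4.1.3 itself puts inflammation and fibrosis in the primary objective.

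Fourth, a remedy can do harm. The background says that growing visceral fat worsens insulin resistance and so leads to steatosis and inflammation. Liver measures entered beside BMI may therefore be mediators, and the BMI coefficient would no longer be obesity's overall association. This stands, and it is why the liver exposure belongs in a separate model.

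**Conclusion.** The point holds as a specification fault that should be corrected before titres are analysed. Read literally, one of the two associations named in the model cannot be estimated, because the exposure is the same in 70 of 70 subjects. Read as severity, it has no definition. Either way, the inflammation/fibrosis part of the primary objective has no defined adjusted estimate. This conclusion rests on the text alone; only the precision figures depend on assumed prevalence, shared variance and response rates.

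Two stronger conclusions might be drawn and are not supported. One is that the regression as a whole, or the obesity hypothesis, is compromised: the obesity coefficient does not change when the constant term is dropped. The other is that the sponsor certainly meant presence versus absence of NAFLD: the document leaves room for severity.

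**What to change.** Amend the last sentence of section 4.1.3 as follows.

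1. **Obesity model.** Keep it as planned (obesity, age, co-morbidities), with sex as in the section's other adjustment list and without liver terms.
2. **Fibrosis model.** Replace the NAFLD term with a second, separate model. The exposure is at least moderate fibrosis at baseline, yes/no, from biopsy where done and otherwise from elastography. Write down the qualifying biopsy stage and one stiffness cut-off before titres are seen, for this analysis only. Fit it to month-7 log10 anti-HBs titre, adjusted for BMI, age, sex and diabetes, and state how titres below the assay limit are handled. The logistic version at 10 mIU/ml is secondary because non-responders may be few.
3. **Inflammation.** Before titres are seen, name one marker already collected (ferritin or a transaminase, for example; the choice is the sponsor's) and analyse it in the same way.
4. **Measurement.** Because biopsy depends on elastography failure or raised stiffness, report the measurement method and missing fibrosis data by BMI group, and repeat the analysis with elastography only.
5. **Scope.** State that no within-study NAFLD-versus-no-NAFLD effect can be estimated and that comparison with outside healthy-adult trials is descriptive.

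The cost is plan wording and analysis code, with no added visit, sample or subject. The downsides are the wide intervals shown above, information lost by a yes/no fibrosis variable, and a blood marker that is only a surrogate for liver inflammation.
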